14.4 Statistical Methods

Demographics and baseline characteristics of patients will be summarized using descriptive statistics. No imputation for missing values is intended. All statistical tests comparing the two arms will be 2-sided, 5% alpha will be used and no adjustment for multiplicity is intended.

14.5 Safety Analysis

Safety will be assessed using CTCAE v4.03 and the maximum toxicity grade per patient of each adverse event will be derived and presented in table format according to arm and overall. The number of patients who suffer from grade 3 or higher toxicities (for each toxicity type and overall) will be provided considering all patients who have received at least one dose of pembrolizumab and completed at least one SABR treatment. The safety analysis will be conducted twice: once for all AE's, regardless of relatedness to treatment and once considering only AE's related to the treatment (i.e. classified as possibly, probably or definitely related).

14.6 Time-to-Event Endpoint Analysis

A cut-off date for follow-up will be determined at the time of analysis. The cut-off date will be chosen to enable data on follow-up to that date to be collected, where possible, on all living patients. All events occurring after this date will be ignored in the analysis in order to minimise reporting bias. Progression free survival and overall survival will be described for each arm using Kaplan-Meier methods. Estimates at key time points will be provided with 95% confidence interval. Stratified log-rank test will be used to compare the curves between arms.

An event history chart will be used to describe the individual patient's events of interest. Each patient in each arm will be represented as a line with different symbols identifying when the patient had a progression on irradiated lesions, progression on a non-irradiated lesions, appearance of new lesions, when treatment ceased, when they died and when censoring occurred.

14.7 Response Analysis

All tumour response measurements (pre- and post-treatment) must be recorded using the definitions of RECIST 1.1. RECIST assessments will take into account post-treatment inflammatory processes that occur after SABR treatment in pulmonary and liver tissues. PET response criteria will also be assessed and reported. If a criterion is met in more than one response type then the response type will be classified at the lowest possible level. The initial assessment of response will be determined after all protocol treatment has been completed, whether or not all of the planned treatment was received. In addition, irRECIST, PERCIST and Peter Mac Metabolic Response criteria will be considered in conjunction to RECIST 1.1. Metabolic response criteria and PERCIST 1.0 results or assessments will not be entered by site clinical staff and will be reported centrally. Overall patient's response rates

(CR+PR at all lesions) at 6 and 12 months after commencement of SABR treatment will be described as percentages with exact 95% confidence interval. Overall response for all irradiated lesions and un-irradiated lesions will also be assessed separately. Lesion size of measurable lesions may be plotted over time to describe patient response trajectories. Overall response rates will be compared between treatment arms using Fisher's exact test.

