6. Biochemistry: calcium chloride, glucose, phosphorus, potassium, sodium, magnesium, total protein, Liver Function Tests: Albumin, Alkaline Phosphatase (ALP), Alanine Aminotransferase (ALT), Aspartate Aminotransferase (AST), Lactate Dehydrogenase (LDH), Gamma-Glutamyl Transferase (GGT), total bilirubin (+direct bilirubin if total bilirubin is elevated above the ULN), Kidney Function Tests: Urea, creatinine.
7. Thyroid Function tests: T3, T4 and TSH. To be performed at during screening, day 1 cycle and every 6 weeks thereafter.
8. Coagulation Profile: PT (INR), aPTT.
9. Virology: HIV, Hepatitis B and C tests only required for those patients at risk of prior or current active infection as determined by the investigator. To be performed within 21 days of randomisation.

Tumour evaluation

10. Radiological tumour assessments will be performed by CT scan (or MRI as required if tumour is in extremity) at screening (within 6 weeks of randomisation), prior to cycle 3, 5, 7 and every 3 cycles thereafter in the treatment phase. Then 3 monthly in the follow-up phase until the last patient recruited completes 24 months of follow-up, unless evidence of progression earlier. Whole body bone scan (WBBS) will be performed if clinically indicated at the same time points. Formal response assessment (using RECIST 1.1, irRECIST, Peter Mac Metabolic Response Criteria and PERCIST 1.0.) at each scheduled scan time point. Response should be confirmed with repeat imaging 4 to 8 weeks later by the same imaging modality. CT of brain only required at screening.
11. FDG PET at baseline and prior to cycle 5 of pembrolizumab. (note: a contemporaneous CT brain/chest/abdo pelvis performed at the same time will fulfill the CT requirement 3 month follow-up)

Biological Evaluations

12. A fresh biopsy of the primary or metastatic lesion will be performed at screening (within 12 weeks of randomisation). and 3 months post completion of SABR. This will ideally be the same site as biopsied before at screening. In event of disease progression, a sample from progressing metastatic site(s), if feasible, is requested. Refer to the SABRseq laboratory manual for further details on handling and shipping of tumour samples.

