Eligible patients will be randomised to either:

Arm 1: SABR followed by pembrolizumab; *or*

Arm 2: Pembrolizumab followed by SABR after cycle 1

Refer to Trial Schema

Pembrolizumab at a dose of 200 mg will be delivered every 3 weeks for a total duration of 102 weeks (34 cycles), commencing either 7 days (+/- 2 days) before the first dose of SABR or 7 days (+/-2 days) after the last dose of SABR.

Tumour response will be assessed according to RECIST 1.1, and irRECIST, Peter Mac Metabolic Response Criteria and PERCIST 1.0. Responses will be characterized in lesions treated with SABR and in un-irradiated lesions.

Peripheral blood samples and where possible, tumour tissue will be collected pre, during and post-treatment to assess baseline findings and longitudinal changes in immune subsets within tumour tissue and peripheral blood.

Evaluable patients are those that receive at least one dose of pembrolizumab and one dose of SABR. Non-evaluable patients will be replaced until the planned sample size has been reached.

7. Study Population

Patients with metastatic NSCLC who meet the inclusion/exclusion criteria described below will be eligible for participation in this study.

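### Section 14.7 dates the initial response assessment from the end of all protocol treatment, which contradicts its own 6- and 12-month rates, the on-treatment scan schedule and the interim PET analysis

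*Combined protocol and SAP*

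**What the plan says.** Section 14.7 states: "The initial assessment of response will be determined after all protocol treatment has been completed". It adds that this applies even when some planned treatment was not given. Pembrolizumab is part of protocol treatment, and section 6 gives it "every 3 weeks for a total duration of 102 weeks (34 cycles").

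Other parts of the document set different times for response:

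- **Section 14.7, same paragraph:** overall CR+PR rates "at 6 and 12 months after commencement of SABR treatment", with exact 95% confidence intervals. Overall response rates are compared between arms by Fisher's exact test.
- **Footnote 10 to Tables 1 and 2:** imaging "prior to cycle 3, 5, 7 and every 3 cycles thereafter in the treatment phase", and "Formal response assessment (using RECIST 1.1, irRECIST, Peter Mac Metabolic Response Criteria and PERCIST 1.0.) at each scheduled scan time point".
- **Section 8.2.3 (Arm 1):** response assessment at those same cycles, without condition.
- **Section 8.3.3 (Arm 2):** the same cycles, but CT and response assessment depend on clinical indication.
- **Footnote 11:** FDG-PET at baseline and before cycle 5 only.
- **Section 14.9:** an interim analysis of PET response once all patients have completed 5 cycles.

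**The concern.** The rules cannot all be followed for a patient who is still on pembrolizumab at 6 or 12 months. Section 14.7 says that such a patient has no initial response yet. The next part of the same paragraph needs that patient's response status.

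If an analyst applied the sentence as written, the time of first assessment would depend on how the patient did. A patient who stops early would be assessed early. A patient who responds and stays on treatment would be assessed at about two years. Continuing responders would then have no response on record at either landmark. Response is a secondary endpoint, but it is compared between arms of 16, so each patient misclassified or left out of a full arm moves that arm's rate by up to 1/16 = 6.25 percentage points.

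**Working it through.** **Inputs.** 34 cycles at 3-week intervals (section 6). SABR 7 days before cycle 1 in Arm 1 and 7 days after it in Arm 2, each ±2 days (section 6). Scans before cycles 3, 5, 7 and every third cycle after that (footnote 10). First follow-up visit 3 months ±7 days after the last cycle (Tables 1 and 2). The timings assume no dose delays and SABR on one day.

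**The plan's duration.** 34 × 3 = 102 weeks (23.5 months), which reproduces the stated figure. Day 1 of cycle k falls at week 3(k − 1), so the last dose is at 3 × 33 = week 99 (22.8 months).

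**On-treatment scans.** They fall before cycles 3, 5, 7, 10, 13, 16, 19, 22, 25, 28, 31 and 34, at weeks 6, 12, 18, 27, 36, 45, 54, 63, 72, 81, 90 and 99. All 12 come before treatment is complete, including the one before the final dose.

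**First assessment under the literal rule, full-course patient.** The 30-day safety visit has no response assessment in Tables 1 and 2 or in section 8.4. The next scheduled response scan is 3 months (13 weeks) after the last cycle: 99 + 13 = about week 112 from cycle 1. Counted from SABR, that is week 113 in Arm 1 and week 111 in Arm 2.

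**Distance from the landmarks.** 6 months = 365.25/2/7 = 26.1 weeks; 12 months = 365.25/7 = 52.2 weeks.

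- After the 6-month landmark: 113 − 26.1 = 86.9 weeks (Arm 1) and 111 − 26.1 = 84.9 weeks (Arm 2), about 20 months.
- After the 12-month landmark: 113 − 52.2 = 60.8 weeks (Arm 1) and 111 − 52.2 = 58.8 weeks (Arm 2), about 14 months.
- A patient dosed on schedule has had 9 (Arm 1) or 10 (Arm 2) of 34 doses at 6 months and 18 at 12 months. Both landmarks therefore fall during treatment.

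**An early stopper for comparison.** Take a patient whose last dose is cycle 4 (week 9) and who stops for a reason other than progression. The 3-month follow-up scan falls at 9 + 13 = week 22. Section 7.6 also mentions efficacy at the 30-day visit for patients who stop early; that would be about 9 + 4 = week 13. Either is about 90 weeks or more before the full-course patient's assessment.

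**PET.** The PET before cycle 5 falls at week 12, and the interim analysis depends on it. No PET is scheduled after treatment, so for a full-course patient the literal rule could not be applied to PERCIST or the Peter Mac criteria at all.

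**What the existing schedule supplies.** Weeks from SABR at the nominal 7-day interval:

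| Landmark | Nearest scan | Arm 1 | Arm 2 |
|---|---|---|---|
| 6 months (26.1) | before cycle 10 (week 27) | 27 + 1 = 28 | 27 − 1 = 26 |
| 12 months (52.2) | before cycle 19 (week 54) | 54 + 1 = 55 | 54 − 1 = 53 |

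By 6 months there are three assessments in Arm 1 and four in Arm 2. By 12 months there are six in each arm. The furthest landmark scan is 55 − 52.2 = 2.8 weeks late. If SABR in Arm 1 is spread over the 7 days that section 9.1 allows, that arm's scans move about 1 week later. Section 14.7 gives no window for either landmark.

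**The case against.** The strongest reply is that no harm need follow. Section 14.7 does not say that response is assessed only at the end of treatment, and it does not tell the analyst to discard on-treatment scans. It ties the landmark rates to the start of SABR, not to an initial assessment. The clause about incomplete treatment suggests that the sentence was meant to keep partly treated patients in the analysis. It might also have been meant to refer to SABR alone.

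Part of this stands. A reader might infer that the 6- and 12-month rates are impossible to obtain, or that no response data exist until treatment ends. The documents do not support either inference: footnote 10 and section 8.2.3 schedule the assessments, and the scans before cycles 10 and 19 lie close to both landmarks.

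The benign readings of the sentence are possible, but the text states neither of them. It refers to all protocol treatment, and pembrolizumab is plainly part of that. A sentence that has to be set aside for the rest of its own paragraph to work should be corrected.

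It is also fair that response is a secondary endpoint in a 32-patient Phase Ib trial whose primary endpoint is toxicity. The toxicity probabilities in Table 9 and the confidence intervals in Table 10 do not depend on this point.

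**Conclusion.** The sentence in section 14.7 is wrong as written. It conflicts with the landmark rates in its own paragraph, with footnote 10 and section 8.2.3, and with the interim analysis in section 14.9. Followed literally, it would put a full-course patient's first response at about week 112 and make assessment time depend on outcome.

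The defect is in the analysis rule. Under footnote 10 the data for both landmarks are already scheduled, at about weeks 26 to 28 and 53 to 55 after SABR. These timings assume on-schedule dosing, the nominal 7-day interval and single-day SABR.

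The place where data could actually be missing is section 8.3.3. If its clinical-indication condition governs, Arm 2 could have fewer landmark assessments than Arm 1, and the comparison between arms would suffer. The documents do not say which text takes precedence.

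The correction should be made before the response analysis. It changes no sample-size figure and leaves the primary endpoint untouched.

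**What to change.** Replace the sentence in section 14.7 with:

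> RECIST 1.1 and irRECIST response is assessed from the scan before cycle 3 and at every scheduled scan thereafter, and metabolic response (PERCIST, Peter Mac) at the PET before cycle 5, whether or not protocol treatment is continuing or was fully received. The 6- and 12-month rates use the scheduled scans nearest those landmarks (before cycles 10 and 19 for patients on treatment).

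The two kinds of criteria are separated because PET is scheduled only at baseline and before cycle 5, although footnote 10 names all four methods at every scan. State an acceptance window around each landmark; it needs to allow for the roughly 3-week lag in Arm 1 at 12 months, and about 1 week more if SABR is spread over several days.

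Reconcile section 8.3.3 with footnote 10 and section 8.2.3 so that both arms are assessed on the same schedule.

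The cost is a few lines of wording. No new scans are needed under the footnote 10 schedule. If sites have been following section 8.3.3 in Arm 2, the reconciliation could add scans in that arm.

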5.2 Objectives

Primary objective:

To assess common toxicities associated with pembrolizumab in combination with SABR when SABR is given before or after first cycle of pembrolizumab in patients with metastatic NSCLC.

Secondary objectives:

Secondary objectives are to examine the clinical efficacy of the combination:

- To describe response rate in: a) lesions treated with SABR, b) non-irradiated lesions and c) overall response, and compare between treatment arms
- To describe overall survival (OS) and progression free survival (PFS) and compare between treatment arms
- To describe the event history (progression at an irradiated lesion, progression at a non-irradiated lesion, appearance of a new lesion, ceasing treatment and death) of NSCLC patients treated with SABR in combination with pembrolizumab

Exploratory Objectives

- Evaluate PD-L1 expression in baseline tissue using immunohistochemistry.
- Evaluate baseline and longitudinal cellular and molecular changes in archival tumour tissue, and/or fresh tumour biopsies. This will include tumour infiltrating lymphocytes (TILs), CD73 and other markers.
- Evaluate longitudinal changes in immunological cellular subsets and cytokines within peripheral blood.

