14.2 Treatment Assignment

Patients will be randomised in the ratio of 1:1 between the two arms. Once randomisation is assigned, cancellation will not be permitted. Patients will be stratified by number of metastases to be treated with SABR (two groups: 1 metastasis vs 2 or 3 metastases), and by line of therapy (two groups: previously treated vs previously untreated).

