14.9 Sample Size Calculation

This is a Phase Ib study with a sample size of 32 patients (16 in each arm). This study will assess the common toxicities associated with the combination of SABR and pembrolizumab. The sample size was determined such that, within each arm, the probability of observing toxicity in at least one patient was 80% for toxicities with true incidence rates of at least 10%. Table 9 illustrates different scenarios for true toxicity rates ranging from 5% to 30% with the respective probability of at least one patient presenting with the toxicity within the arm and overall.

Table 9: Probability of at least one patient presenting with a toxicity for different true toxicity rates

True toxicity rate	Within each arm (n=16)	Overall (n=32)
5%	0.560	0.806
10%	0.815	0.966
15%	0.926	0.994
20%	0.972	0.999

The table below shows the expected confidence interval for different response rate scenarios within each arm.

Table 10: Response rate and confidence intervals for different number of responses with n=16

Number of responses	Response rate (95% confidence interval)
6	37.5 (15 – 65)
8	50 (25 – 75)
10	62.5 (35 – 85)
12	75 (48 – 93)

Recruitment will occur over a two-year period. The principal analyses will be 24 months after the last patient has commenced treatment. An interim analysis assessing patterns of failure

and response to therapy based on post-therapy PET response will be performed once all recruited patients have completed 5 cycles of pembrolizumab therapy.

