3.5 RECIST 1.1 Response Criteria

	Target lesions	Non-target lesions
Complete Response (CR)	Disappearance of all target lesions. Any pathological lymph nodes (whether target or non-target) must have reduction in short axis to <10 mm	Disappearance of all non-target lesions and normalisation of tumour marker level. All lymph nodes must be non-pathological in size (<10 mm short axis)
Partial Response (PR)	At least a 30% decrease in the sum of diameters of target lesions, taking as reference the baseline sum diameters	Persistence of one or more non-target lesion(s) or/and maintenance of tumour marker level above the normal limits
Progressive Disease (PD)	At least a 20% increase in the sum of diameters of target lesions, taking as reference the smallest sum on study (this includes the baseline sum if that is the smallest on study). In addition, the sum must also demonstrate an absolute increase of at least 5 mm. The appearance of one or more new lesions is also considered progression.	Appearance of one or more new lesions and/or unequivocal progression of existing non-target lesions (1)

Stable Disease (SD)	Neither sufficient shrinkage to qualify for PR nor sufficient increase to qualify for PD, taking as reference the smallest sum diameters while on study.	
(1) Although a clear progression of "non target" lesions only is exceptional, in such circumstances, the opinion of the treating physician should prevail and the progression status should ideally be confirmed later on by the review panel (or Study Chair).		

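### Between-arm response is tested only as CR+PR yes/no with Fisher's exact test; a pre-specified comparison of the ordered RECIST category would be a cheap improvement

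*Combined protocol and SAP*

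**What the plan says.** Section 5.2 lists response as a secondary objective in three parts: irradiated lesions, non-irradiated lesions, "c) overall response, and compare between treatment arms". Section 14.7 requires pre- and post-treatment tumour measurements to be recorded under RECIST 1.1. It summarises response as CR+PR at 6 and 12 months after the start of SABR, with exact 95% intervals, and then states: "Overall response rates will be compared between treatment arms using Fisher's exact test". The measurements have one further use, which is optional: "Lesion size of measurable lesions may be plotted over time to describe patient response trajectories".

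Appendix 3, section 3.5, defines partial response as a cut in a continuous quantity ("At least a 30% decrease in the sum of diameters of target lesions, taking as" reference the baseline sum) and sets out CR, PR, SD and PD as an ordered scale.

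On testing, section 14.4 says "All statistical tests comparing the two arms will be 2-sided, 5% alpha will be used and no adjustment for multiplicity is intended". On size, section 14.9 says "This is a Phase Ib study with a sample size of 32 patients (16 in each arm"), and the number was chosen so that, within an arm, "the probability of observing toxicity in at least one patient was 80% for toxicities with true incidence rates of at least 10"%. No between-arm difference in response, and no power for one, is stated.

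**The concern.** Under CR+PR yes/no, a patient with 29% shrinkage counts the same as one who progressed or died, and one with 31% shrinkage counts the same as one whose disease disappeared. The trial records these distinctions and then leaves them out of its only test of response between the sequences. Nothing in the documents gives a reason for stopping at that cut; Appendix 3 defines the categories but does not say how two arms should be compared on them.

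With 16 v 16 patients, unused information is costly, and Fisher's test is conservative as well. At stake is a secondary comparison of the two sequences. Section 4.13 expects the findings to serve as the basis for larger randomised studies, so an estimate that uses the whole response scale would be worth having.

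**Working it through.** **Plan's own figures.** Table 9 reproduces: with a true rate of 10%, 1 − 0.9^16 = 0.815 and 1 − 0.9^32 = 0.966. Table 10 reproduces with Clopper-Pearson intervals at n = 16: 6 responses give 15.2 to 64.6%, 8 give 24.7 to 75.3%, 10 give 35.4 to 84.8% and 12 give 47.6 to 92.7%. Neither table concerns a difference between arms.

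**Inputs.** n = 16 per arm (14.9), 1:1 allocation (14.2), two-sided 5% (14.4). Response rates are taken from Table 10 in pairs. This is an assumption, since Table 10 gives single-arm precision scenarios.

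**Binary tests.** Power = Σᵢ Σⱼ b(i; 16, p₁) b(j; 16, p₂) × 1{p-value(i, j) ≤ 0.05}, summed over all 17 × 17 outcomes. It was computed for Fisher and for Boschloo's unconditional exact test, so that the loss due to Fisher's conservatism is kept apart from the loss due to the cut. With 37.5% in both arms, Fisher's actual size is 1.9%.

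**Ordered comparison.** Two-sided Wilcoxon rank-sum on death/PD < SD < PR < CR, tie-corrected, with 40,000 simulated trials per scenario. In the lower-response arm, 20%, 40% or 58.8% were placed in the worst category where the non-responder share allows it. The 58.8% is 100 − 19.4 − 21.8, from the response and stable-disease rates in section 4.12. CR was set at a tenth of responders or at 1.5 SD above the response cut. Two models were used:

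- *Shift.* The whole distribution of tumour change moves by z(p₂) − z(p₁): 0.64 SD for 37.5 v 62.5%, 0.67 for 50 v 75%, 0.99 for 37.5 v 75%.
- *Rate only.* The share of responders changes, but the mix within responders and within non-responders does not.

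Example for 37.5 v 62.5% with 40% worst: the lower arm is 40 / 22.5 / 33.8 / 3.8% (death or PD / SD / PR / CR). Under rate only, the non-responder shares are multiplied by 0.375/0.625 = 0.6 and the responder shares by 0.625/0.375 = 1.67, giving 24 / 13.5 / 56.2 / 6.2%.

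| Rates | Fisher | Boschloo | Ordered, shift | Ordered, rate only |
|---|---|---|---|---|
| 37.5 v 50% | 5% | 9% | 11–12% | 9–10% |
| 62.5 v 75% | 5% | 9% | 13–14% | 10% |
| 37.5 v 62.5% | 18% | 26% | 32–35% | 25–27% |
| 50 v 75% | 18% | 28% | 37–38% | 26–27% |
| 37.5 v 75% | 44% | 55% | 66–69% | 52–54% |

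With equal rates of 37.5%, the ordered test rejects in 4.6 to 4.9% of simulated trials.

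**Reading the table.** For 37.5 v 62.5%, the move from Fisher to Boschloo is worth 26 − 18 = 8 points. The ordered scale then adds 32 − 26 = 6 to 35 − 26 = 9 points under shift, and −1 to +1 under rate only. For 37.5 v 75%, the first step is 55 − 44 = 11 points. The second is 66 − 55 = 11 to 69 − 55 = 14 under shift, and −3 to −1 under rate only.

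**Ranking by percentage change instead.** With 40% tied worst, the shift model gives 37%, 41% and 73% for the last three rows. Under rate only it falls 2 to 11 points below Boschloo and roughly matches Fisher or slightly exceeds it. It is therefore more sensitive to the model than the ordered categories are.

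**The case against.** The case for leaving the plan alone is substantial. The comparison is secondary in a Phase Ib trial sized for toxicity, no power is claimed for it, and no decision is tied to its p-value. CR+PR with exact intervals is familiar and already planned. Progression and death are already compared without a cut, by stratified log-rank tests on PFS and OS (14.6), and a rank that puts both at the bottom partly repeats PFS. All of this stands, and it limits the weight of the point. It does not explain why a more conservative test on less information is preferred.

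Three stronger readings are tempting, and the documents support none of them.

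- *That the cut costs a fixed number of power points.* No effect or outcome model is stated. Against a better binary test, the gain runs from 14 points to slightly below zero, depending on the model.
- *That percentage change in tumour size could be ranked for every lesion set from data in hand.* Section 7.1 requires a measurable lesion only among those not planned for SABR. Bone may be irradiated (9.3), and Appendix 3 counts bone as measurable only with a soft-tissue component of at least 10 mm. Section 14.7 itself warns of inflammation after SABR in lung and liver. An irradiated-lesion sum may be missing or distorted.
- *That the efficacy comparison rests on response.* PFS and OS are compared as well.

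Stratification also has a cost in a trial this small: two binary factors make four strata, or 32/4 = 8 patients each on average. With four equal strata and no stratum effect, a stratified rank test on percentage change gave 36%, 39% and 70% under shift, against 37%, 41% and 73% unstratified. The stratified ordered-category test was not simulated.

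**Conclusion.** The point holds as a cheap improvement. In every scenario examined the ordered-category comparison has more power than the planned Fisher test: by about 14 to 25 points for differences of 25 points or more under a shift in depth of response, and by about 7 to 10 points if only the response rate changes. Much of that comes from Fisher's conservatism. Relative to Boschloo's test, the ordered scale gains 6 to 14 points under shift and is about level or up to 3 points lower under rate only. For 12.5-point differences every test here has power below about 15%, and no ordered-scale scenario reaches 80%.

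These figures rest on Table 10 rates used as assumed effects, on the two outcome models, on the assumed split between categories, on complete data and on an unstratified test. A reader should not infer that the trial's conclusions are in danger or that the planned test is invalid. It is valid but conservative, and it sets aside recorded information.

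**What to change.** In section 14.7:

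1. Keep the CR+PR rates with exact 95% intervals as the descriptive summary.
2. Pre-specify, for overall response at 6 and 12 months, a Wilcoxon rank-sum comparison of the ordered category: death or progression by that time worst, then SD, PR, CR. Stratify by the two randomisation factors where the strata allow, and state beforehand what is done when they do not. Report the probability that a patient in one arm has the better outcome, with a 95% interval.
3. Keep the responder comparison as supportive.
4. Make ranking by percentage change in the sum of diameters a sensitivity analysis, for overall and non-irradiated measurable lesions only.
5. State how a patient with a missing scan and no progression is handled, with the same rule as for CR+PR. Section 14.4 plans no imputation, and section 14.3 limits the response population to patients scanned at the visit, so the text must say that patients who died or progressed earlier stay in the ranking.
6. Reconcile section 8.3.3, which makes Arm 2 CT/MRI and response assessment conditional on clinical indication, with footnote 10 to Tables 1 and 2, which schedules them in both arms. Either analysis depends on this.

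The cost is one paragraph of text and a few lines of code, with no new scans, readers or patients. The drawbacks are a less familiar effect measure and one more secondary test in a set already declared unadjusted for multiplicity.
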